7.4 Assignment of Adverse Event Intensity and Relationship to Investigational Product

The following categories and definitions of causal relationship to investigational product as determined by a physician should be used:

- **Unrelated:** The cause of the AE is known and the event is in no way related to any aspect of study participation. If there is any uncertainty regarding AE causality then the event must be assessed as possibly related to research participation and reported to the IRB as indicated. Often, the cause of an unrelated AE is disease progression.
- **Possibly Related:** An AE is possibly related when there is a reasonable possibility that the event might have been caused by study participation. A possibly related event may follow no known pattern of response and an alternative cause seems more likely. In other circumstances there may be significant uncertainty about the cause of the event, or a possible relationship to study participation cannot reasonably be ruled out.
- **Probably Related:** An AE is probably related when there is a reasonable possibility that the event is likely to have been caused by study participation. The AE has a timely relationship to the study procedure(s) and follows a known pattern of response, but a potential alternative cause may be present.
- **Definitely Related:** An AE is definitely related to study participation if it is clear that the event was caused by study participation. A definitely related event has a strong temporal relationship and an alternative cause is unlikely.

7.5 Collection and Reporting

Adverse events can be spontaneously reported or elicited during open-ended questioning, examination, or evaluation of a subject. (In order to prevent reporting bias, subjects should not be questioned regarding the specific occurrence of one or more AEs.)

If known, the diagnosis of the underlying illness or disorder should be recorded, rather than its individual symptoms. The following information should be captured for all AEs: onset, duration, intensity, seriousness, relationship to investigational product, action taken, and treatment required. If treatment for the AE was administered, it should be recorded in the medical record.

The investigator shall supply the sponsor and Ethics Committee with any additional requested information, notably for reported deaths of subjects.

7.5.1 Handling of Expedited Safety Reports

In accordance with local regulations, BMS and Dendreon will notify investigators of all SAEs that are suspected (related to the investigational product) and unexpected (i.e., not previously described in the Investigator Brochure). Investigator notification of these events will be in the form of an expedited safety report (ESR).

Other important findings which may be reported by the sponsor as an ESR include: increased frequency of a clinically significant expected SAE, an SAE considered associated with study procedures that could modify the conduct of the study, lack of efficacy that poses significant hazard to study subjects, clinically significant safety finding from a nonclinical (e.g., animal) study, important safety recommendations from a study data monitoring committee, or sponsor decision to end or temporarily halt a clinical study for safety reasons.

Upon receiving an ESR from BMS, the investigator must review and retain the ESR with the Investigator Brochure. Where required by local regulations or when there is a central IRB/IEC for the study, the sponsor will submit the ESR to the appropriate IRB/IEC. The investigator and IRB/IEC will determine if the informed consent requires revision. The investigator should also comply with the IRB/IEC procedures for reporting any other safety information.

7.5.2 Non-serious Adverse Events

The collection of non-serious AE information should begin at initiation of investigational product. If an ongoing non-serious AE worsens in its intensity, or if its relationship to the investigational product changes, a new non-serious AE entry for the event should be completed. Non-serious AEs should be followed to resolution or stabilization, or reported as SAEs if they become serious. Follow-up is also required for non-serious AEs that cause interruption or discontinuation of investigational product, or those that are present at the end of study participation. Subjects with non-serious AEs at study completion should receive post-treatment follow-up as appropriate.

All identified non-serious AEs must be recorded and described in the medical record.

7.5.3 Pregnancy

Study participants must use an effective method of birth control during the course of the study, in a manner such that risk of failure is minimized. Before study enrollment, study participants and their partners must be advised of the importance of avoiding pregnancy during study participation and the potential risk factors for an unintentional pregnancy. The study participant must sign an informed consent form documenting this discussion.

Any pregnancy that occurs in a female partner of a male study participant should be reported to the sponsors.

7.6 Data Safety Monitoring Plan

Safety assessments will consist of monitoring and recording all adverse events and serious adverse events, the regular monitoring of hematology, blood chemistry and urine values, regular measurement of vital signs and the performance of physical examinations.

7.6.1 Oversight and Monitoring Plan

The UCSF Helen Diller Family Comprehensive Cancer Center (HDFCCC) Data and Safety Monitoring Committee (DSMC) is responsible for monitoring data quality and subject safety for all HDFCCC institutional clinical studies. A summary of DSMC activities for this study include:

- Review of subject data
- Review of suspected adverse reactions considered “serious”
- Monitoring every six months (depending on study accrual)
- Minimum of a yearly regulatory audit

7.6.2 Monitoring and Reporting Guidelines

Investigators will conduct continuous review of data and subject safety and discuss each subject’s treatment at monthly Site Committee meetings. These discussions are documented in the Site Committee meeting minutes. The discussion will include the number of subjects, significant toxicities in accordance with the protocol, and observed responses.

All institutional Phase 2 or 3 studies are designated with a moderate risk assessment. The data is monitored twice per year with twenty percent of the subjects monitored (or at least three subjects if the calculated value is less than three). The participating site(s) will submit the source documents electronically for the UCSF DSMC to perform remote monitoring and source document verification as per the attached Data and Safety Monitoring Plan for Multicenter Studies (Phase 2 or 3 Institutional Study) (Appendix 8).

7.6.3 Review and Oversight Requirements

7.6.3.1 Adverse Event Monitoring

All grade(s) 3-5 adverse events, whether or not unexpected, and whether or not considered to be associated with the use of the study drug, will be entered into OnCore®, UCSF’s Clinical Trial Management System.

All grade(s) 3-5 adverse events entered into OnCore® will be reviewed on a monthly basis at the Site Committee meetings. The Site Committee will review and discuss the selected toxicity, the toxicity grade, and the attribution of relationship of the adverse event to the administration of the study drug(s).

In addition, all suspected adverse reactions considered “serious” entered into OnCore®, will be reviewed and monitored by the Data and Safety Monitoring Committee on an ongoing basis and discussed at DSMC meetings, which take place every six weeks.

If a death occurs during the treatment phase of the study or within 30 days after the last administration of the study drug(s) and it is determined to be related either to the study drug(s) or

to a study procedure, the Investigator or his/her designee must notify the DSMC Chair within 1 business day of knowledge of this event. The contact may be by phone or e-mail.

7.6.3.2 SAE Reporting

The principal investigator has the obligation to report all serious adverse events to the UCSF IRB, Bristol-Myers Squibb Company Global Pharmacovigilance and Epidemiology department, and Dendreon Pharmacovigilance (PV).

Bristol-Myers Squibb Company Global Pharmacovigilance and Epidemiology department

SAEs should be reported on the MedWatch form 3500A, which can be accessed at:

<http://www.accessdata.fda.gov/scripts/medwatch/>

MedWatch SAE forms should be sent to the FDA at:

MEDWATCH [REDACTED]
[REDACTED]

All SAEs should be simultaneously faxed or e-mailed to BMS at:

Global Pharmacovigilance & Epidemiology Bristol-Myers Squibb Company [REDACTED]
[REDACTED]

All SAEs that occur from the signing of the Study-specific consent through the duration of the post-therapy adverse event collection period must be reported to Dendreon within 24 hours of being made aware of the SAE. Notification can be made via phone or telefacsimile using an SAE Report Form to be provided by Dendreon (Form is provided in Appendix 10). Sponsor shall notify institution, investigator and IRB immediately during the conduct of the study and/or after the study is completed should it become aware of information related to the study that would impact participant safety or clinical care. Institution shall promptly disclose such information to study participants.

Dendreon Corporation

Attn: Safety Manager

[REDACTED]

[REDACTED]

Significant new information regarding an ongoing SAE and the resolution must be sent to Dendreon within 3 business days of awareness of the new information to Dendreon on the SAE Report Form

Any Serious Adverse Event (SAE) will be reported to the local institution's IRB and the UCSF GU Medical Oncology Clinical Research Program as specified below. Serious Adverse events will be reported on the MedWatch form. The date the SAE was sent to all required reporting agencies will be documented on OnCore, hard copies of the report will be maintained in the regulatory files. UCSF will circulate all SAE's to the participating centers.

Any adverse event falling under the definition of Serious will be reported immediately to the Study Chairman who, in turn, must notify the UCSF IRB per IRB policy. Symptoms related to

progressive disease such as severe bone pain will not be reported as toxicity or as Serious Adverse Events.

UCSF IRB website for guidance in reporting serious adverse events:

http://www.research.ucsf.edu/chr/Guide/chrA_AE.asp

MedWatch forms and information: <http://www.fda.gov/medwatch/getforms.htm>

Multi-center sites participating in the study will notify the UCSF GU Medical Oncology Clinical Research Program [REDACTED] of all serious adverse events within 24 hours of knowledge of the event. The UCSF clinical research staff will immediately notify the principal investigator (PI) or his designee of the SAE. The participating institutions will submit the SAE to their own IRB. The participating institution must forward a copy of the report filed with their local IRB to the UCSF Urologic Oncology Clinical Research Program within 5 calendar days. After the UCSF clinical research staff receives and processes the initial SAE report from the participating institution, it will be forwarded to the PI or his designee for review and signature. If the SAE is death, and is determined to be possibly, probably or definitely related to the investigational drug or any research related procedure, the event must be reported to the DSMC Chair or his designee within 24 business hours. The reporting procedure is by personal communication via phone or in person with written documentation of the one-on-one communication via e-mail with a copy of the e-mail to the DSMC Administrator.

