1.2.2.8 Safety of 10 mg/kg Multiple Doses

Based on a review of the program-wide SAE data as previously reported, evidence had suggested that ipilimumab-associated irAEs were dose dependent in frequency, and higher irAE rates had been observed at 10 mg/kg than at lower doses of ipilimumab. Subsequently, this dose-dependent effect was further demonstrated in CA184-022 in which three dose levels of ipilimumab were studied, including 0.3 vs. 3 vs. 10 mg/kg. Table 3 summarizes the overall irAE frequencies by dose from CA184-022 based on safety data from the locked clinical database.

Table 3. Summary of Immune-Related Adverse Events (irAEs) by Treatment Groups – Treated Subjects (CA184-022)

	Number of Subjects (%)		
	Ipilimumab		
	0.3 mg/kg (N=72)	3 mg/kg (N=71)	10 mg/kg (N=71)
Overall irAEs	26.4	64.8	70.4
Grade 3-4	0	7.0	25.4
GI irAEs	16.7	32.4	39.4
Grade 3-4	0	2.8	15.5
Hepatic irAEs	0	0	2.8
Grade 3-4	0	0	2.8
Endocrine irAEs	0	5.6	4.2
Grade 3-4	0	2.8	1.4
Skin irAEs	12.5	45.1	46.5
Grade 3-4	0	1.4	4.2

1.2.2.9 *Neuropathies*

Isolated cases of motor neuropathy of an autoimmune origin have been reported among patients treated with ipilimumab. Three cases have been diagnosed as Guillain-Barre syndrome (GBS), two of which were considered study related. In both cases, the GBS was atypical in nature and more clinically resembled polyneuritis. As of 30 June 2009, 27 cases of neuropathy SAEs have been reported. Of these, 22 were assessed as unrelated to study therapy because alternative etiologies, including brain metastases, spinal cord compression, arterial thrombosis, or platinum-base chemotherapy were identified in almost every case.

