7.1.2 Clinical Response Endpoints

Ipilimumab is expected to trigger immune-mediated responses, which require activation of the immune system prior to the observation of clinical responses. Such immune activation may take weeks to months to be evident. Some patients have had objective volume increase of tumor lesions or other disease parameters within 12 weeks following the start of ipilimumab, which is

subsequently followed by objective clinical responses^{9,45}. Early in the treatment, patients may not have had sufficient time to develop the required immune activation or, in some patients, tumor volume or other disease parameter increases may represent infiltration of lymphocytes into the original tumor or blood. In conventional studies, such tumor volume or relevant laboratory parameter increases during the first 12 weeks of the study would constitute PD and lead to discontinuation of treatment as well as subsequent imaging to detect response, thus disregarding the potential for subsequent immune-mediated clinical response.

Therefore, patients with tumor volume increase detected or lack of laboratory parameter response documentation prior to week 12 but without rapid clinical deterioration should continue on treatment with ipilimumab and continue to be imaged to allow detection of a subsequent tumor response. This will improve the overall assessment of the clinical activity of ipilimumab and will more likely capture its true potential to induce clinical responses. Clinical assessment will be made using PSA response and radiographic response using standard irRC.⁹

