- admission encountered for another life circumstance that carries no bearing on health status and requires no medical/surgical intervention (e.g., lack of housing, economic inadequacy, care-giver respite, family circumstances, administrative).

Note that all pregnancies, regardless of outcome, must be reported to the sponsor on a Pregnancy Surveillance Form, not an SAE form. All pregnancies must be reported and followed to outcome, including pregnancies that occur in the female partner of a male study subject. See **Section 7.5.3 for instructions on reporting pregnancies.**

Following the subject's written consent to participate in the study, all SAEs must be collected, including those thought to be associated with protocol-specified procedures. All SAEs must be collected that occur within 70 days of discontinuation of dosing of the investigational product. If applicable, SAEs must be collected that relate to any later protocol-specified procedure (e.g., a follow-up skin biopsy). The investigator should notify BMS and Dendreon of any SAE occurring after this time period that is believed to be related to the investigational product or protocol-specified procedure.

All SAEs whether related or unrelated to the ipilimumab, must be immediately reported to BMS and Dendreon (by the investigator or designee) within 24 hours of becoming aware of the event. If only limited information is initially available, follow-up reports are required. The original SAE form must be kept on file at the study site. If the SAE occurs at a Participating Institution, the Lead Site must also be notified.

If an ongoing SAE changes in its intensity or relationship to the investigational product, a follow-up SAE report should be sent immediately to the sponsor. As follow-up information becomes available it should be sent immediately using the same procedure used for transmitting the initial SAE report. All SAEs should be followed to resolution or stabilization.

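### Section 7.6.3.2 exempts symptoms attributed to progression from SAE reporting, which contradicts the protocol's own all-SAE rules and may also leave gaps in the grade 3-5 data

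*Combined protocol and SAP*

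**What the plan says.** The exemption is one sentence in 7.6.3.2: symptoms related to "progressive disease such as severe bone pain will not be reported as toxicity or as Serious Adverse Events". It does not say who decides that a symptom comes from progression. It does not require progression to be confirmed, and it makes no exception for events that are high-grade or that lead to hospitalisation or death.

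The other reporting rules do not filter by cause:

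- **7.3.1:** "All SAEs whether related or unrelated to the ipilimumab, must be immediately reported to BMS and Dendreon", within 24 hours. The listed exceptions to the SAE definition are types of hospitalisation, and none concerns progression.
- **7.6.3.2 itself**, for reports to Dendreon: "All SAEs that occur from the signing of the Study-specific consent through the duration of the post-therapy adverse event collection period must be reported".
- **7.3:** an adverse event is defined without regard to causality.
- **7.4**, under the unrelated category: "Often, the cause of an unrelated AE is disease progression".
- **7.6.3.1**, repeated in Appendix 9: "All grade(s) 3-5 adverse events, whether or not unexpected, and whether or not considered to be associated with the use of the study drug" are entered into OnCore.
- **7.2:** any non-serious or serious event from consent through follow-up is reported.

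**The concern.** When a site judges a symptom to be due to progression, 7.6.3.2 tells it to make no SAE report and 7.3.1 tells it to report within 24 hours. A site following the exemption would drop events that other sections make mandatory, and no text says which rule prevails.

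This matters more than usual here. Section 3.2 recommends giving all four ipilimumab doses despite apparent clinical progression if performance status is stable, so such symptoms will arise in patients still on treatment. The trial is open-label, so attribution is made with the arm known. The protocol also accepts that drug effects can resemble disease. Section 5.4.6.1 describes inflammatory reactions at sites suspicious for metastasis, and Appendix 6 says endocrine events may look like brain metastases or underlying disease.

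At stake are the completeness of SAE reports and, on one reading, the by-arm safety tables that serve a secondary objective.

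**Working it through.** The plan gives no figure on this point, so the check is a comparison of the rules.

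**Step 1: apply the rules to the same events.** In each case the site attributes the symptom to progression.

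| Event | 7.6.3.2 exemption | Other rules |
|---|---|---|
| Severe bone pain with inpatient admission | Not an SAE, not toxicity | 7.3.1: SAE, report within 24 hours; 7.4: unrelated AE |
| Grade 3 bone pain, no seriousness criterion met | Not toxicity | 7.6.3.1: enter in OnCore |
| Grade 2 bone pain, not serious | Not toxicity | 7.2: report |

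Row 1 is a direct contradiction. Admission meets an SAE criterion, 7.3.1 expressly covers unrelated SAEs, and no listed exception applies.

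Rows 2 and 3 conflict only if toxicity means adverse event. 7.6.3.1 supports that reading: in describing the Site Committee's review of grade 3-5 adverse events, it speaks of the toxicity, its grade and the attribution of the adverse event as one item. The term is not defined, so this conflict is probable rather than proven.

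**Step 2: trace which outputs depend on these events.**

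- *SAE reports to BMS and Dendreon:* affected directly (row 1).
- *By-arm maximum-grade tables* (Synopsis, Endpoints; 9.3.1.1): affected if toxicity means adverse event.
- *Grade 3-4 rate review for the DSMC* (7.6.4): this counts adverse events with no attribution limit, so it is affected on the same reading.
- *SigAE stopping rule* (7.3.2, 9.2.2): SigAEs must be attributable to therapy. An event attributed to progression is not counted even when reported, so the rule changes only if the attribution is wrong.
- *Primary endpoint and sample size:* not affected.

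**Step 3: illustrate the stopping-rule route, under assumed inputs.** Let p be the true SigAE probability per patient and m the share wrongly attributed to progression. Both are assumptions; the documents give neither. Assume independent patients with at most one SigAE each. The chance of reaching 3 SigAEs among the next 10 patients is P(X ≥ 3), with X ~ Binomial(10, p(1 − m)).

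For p = 0.30 and m = 0.20, p(1 − m) = 0.24, and P(X ≥ 3) = 1 − [0.76^10 + 10(0.24)(0.76^9) + 45(0.24^2)(0.76^8)] = 1 − [0.064 + 0.203 + 0.288] = 0.444 (from unrounded terms).

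| p | m = 0 | m = 0.10 | m = 0.20 | m = 0.30 |
|---|---|---|---|---|
| 0.20 | 0.322 | 0.263 | 0.206 | 0.155 |
| 0.30 | 0.617 | 0.534 | 0.444 | 0.353 |

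These losses come from misattribution. The exemption adds to them only by removing a report through which a wrong attribution might be corrected.

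**The case against.** The best defence is that 7.6.3.2 is a specific exception to general rules, and that the two can be read together: record the event as an unrelated adverse event, but do not call it toxicity or an SAE. For non-serious events that reading is available, which is why the grade 3-5 conflict is stated conditionally. For serious events it fails. 7.3.1 covers unrelated SAEs in terms, lists its exceptions without progression, and does not refer to the exemption.

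There are real safeguards. Section 7.4 requires any event of uncertain cause to be rated possibly related, which would keep many doubtful cases reportable. But no text says that step comes before the exemption, and it does not help when a site is confident and wrong. The definition of progressive disease in 7.1.3.1 requires more than three months from the start of therapy, so an early flare would not meet it; the exemption, however, does not cite that definition.

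A reader might infer more than the documents support:

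- *That no one could ever revisit a wrong attribution.* Section 7.6.2 provides monthly Site Committee discussion of each subject and source verification for 20% of subjects, and the Appendix 2 autoimmunity worksheet is completed at every clinic visit. Also, DSMC review of serious events covers suspected adverse reactions, so SAEs rated unrelated fall outside that stream with or without the exemption.
- *That the SigAE count loses these events outright.* By definition it does so only through misattribution.
- *That 22 of 27 neuropathy SAEs in 1.2.2.9 (81%) shows the scale.* Those are historical ipilimumab data. The alternative causes include arterial thrombosis and platinum-based chemotherapy, and no number due to progression is given. Known CNS metastases are excluded from this trial (4.2). The figure does not measure this problem.
- *That 7.1.2 shows these symptoms may be drug effects.* Its remark that "tumor volume or other disease parameter increases may represent infiltration of lymphocytes into the original tumor or blood" concerns tumor volume and disease parameters, not symptoms. Sections 5.4.6.1 and Appendix 6 are closer support.
- *That the immediate arm would be flattered.* Section 1.3 raises possible extra toxicity with immediate dosing but does not say it would appear as a flare at tumor sites.

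**Conclusion.** The contradiction over SAEs is established from the text: the exemption in 7.6.3.2 cannot be followed together with 7.3.1, the all-SAE rule in 7.6.3.2 and the causality categories in 7.4. The contradiction over grade 3-5 events holds if toxicity means adverse event, the more natural reading of 7.6.3.1 but not a defined one.

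The consequence is inconsistent reporting between sites. Serious events attributed to progression may be missing from SAE reports and, on that reading, from the by-arm grade tables and the grade 3-4 rate review. The size cannot be given, because the documents state neither how often such events are expected nor how often attribution would be wrong. Hiding of drug effects is a risk, partly mitigated by the uncertainty rule in 7.4, and not a demonstrated outcome. The passages should be reconciled; the matter is limited to safety reporting.

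**What to change.** Replace the sentence in 7.6.3.2 with:

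*Disease progression itself is not reported as an AE. Any sign, symptom, hospitalisation or death that meets an SAE criterion, or is grade 3-5, is recorded and reported under 7.3.1 and 7.6.3.1 even if attributed to progression, with that attribution stated.*

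If an exemption for non-serious grade 1-2 symptoms of known disease is wanted, reconcile it with 7.2, which says any such event will be reported; otherwise leave it out.

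The cost is one sentence and a modest number of additional unrelated reports. For SAEs these are already required by 7.3.1. No endpoint, analysis or sample size changes. The SigAE count also stays the same unless an event is later re-attributed to therapy.
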